#### **Events meeting the AE definition**

- Any abnormal laboratory test results (hematology, clinical chemistry, or urinalysis) or other safety assessments (eg, ECG, radiological scans, vital signs measurements), including those that worsen from baseline, considered clinically significant in the medical and scientific judgment of the Investigator (ie, not related to progression of underlying disease).
- Exacerbation of a chronic or intermittent pre-existing condition including either an increase in frequency and/or intensity of the condition.
- New conditions detected or diagnosed after study intervention administration even though it may have been present before the start of the study.
- Signs, symptoms, or the clinical sequelae of a suspected drug-drug interaction.
- Signs, symptoms, or the clinical sequelae of a suspected overdose of either study intervention or a concomitant medication.
- "Lack of efficacy" or "failure of expected pharmacological action" per se will not be reported as an AE or SAE. Such instances will be captured in the efficacy assessments. However, the signs, symptoms, and/or clinical sequelae resulting from lack of efficacy will be reported as AE or SAE if they fulfill the definition of an AE or SAE.
- The signs, symptoms, and/or clinical sequelae resulting from lack of efficacy will be reported as AE or SAE if they fulfill the definition of an AE or SAE. Also, "lack of efficacy" or "failure of expected pharmacological action" also constitutes an AE or SAE.

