
 
• To evaluate the ability of dupilumab in reducing the proportion of patients who require treatment with oral corticosteroids (OCS)
 
• To evaluate safety outcome measures
 
• To evaluate immunogenicity of dupilumab
 
	
 
• Time-to-event and proportion of patients receiving OCS for CSU during the planned treatment period
 
• Percentages of participants experiencing treatment-emergent adverse events (TEAEs) or serious adverse events (SAEs)
 
• Incidence of treatment-emergent anti-drug antibodies (ADA) against dupilumab over time
 

Tertiary/exploratory	

 
• To demonstrate exploratory outcome measures in the urticaria composite score and or its components
 
• To demonstrate exploratory health-related quality-of-life and health status measures
 
• To demonstrate reduction in use of rescue medication
 
	
 
• Time to UAS7 MID response (9.5 to 10.5 points) by Week 12 and Week 24
 
• Change from baseline in the number of itch-free days and/or hive-free days at Week 12 and Week 24
 
• Change in UAS7 in well-controlled patients (UAS <math>\leq</math>6) from Weeks 24 to 36
 
• Change from baseline in EQ-5D-5L (or EQ-5D-Y 5L for <math>\geq</math>6 to <16 years old) at Week 12 and Week 24
 
• Change from baseline in CU-QoL at Week 12 and Week 24
 
• Missed school/work days from baseline at Week 12 and Week 24
 
• Use of antihistamine rescue medication
 
• Total OCS rescue dose prescribed (in mg) during the treatment period
 
• Total OCS rescue intake in days during the treatment period
 

Pharmacokinetic	

 
• To evaluate PK and pharmacodynamic (PD) outcome measures
 
	
 
• Functional dupilumab concentrations in serum and PK profile
 
• Pharmacodynamic response for selected biomarkers (total IgE)
 

a Key secondary endpoint for Study A and B

b Key secondary endpoint for Study C: UAS7 at Week 24 (except EU and EU reference countries, where ISS7 at Week 24 is key secondary endpoint)

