  - An overdose (accidental or intentional) with any NIMP is an event suspected by the Investigator or spontaneously notified by the participant and defined as at least twice the maximum prescribed daily dose, within the intended therapeutic interval. “The circumstances (ie, accidental or intentional) should be clearly specified in the overdose form”.

The definitions of an AE or SAE can be found in Appendix 3 ([Section 10.3](#)).

Adverse event will be reported by the participant (or, when appropriate, by a caregiver, parent, surrogate, or the participant's legally authorized representative).

The Investigator and any qualified designees are responsible for detecting, documenting, and recording events that meet the definition of an AE or SAE and remain responsible for following up AEs that are serious, considered related to the study intervention or study procedures, or that caused the participant to discontinue the study intervention (see [Section 7](#)).

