### **8.3.6 Disease-related events and/or disease-related outcomes not qualifying as AEs or SAEs**

The CSU should be reported as an AE or SAE only if judged by the Investigator to have unexpectedly worsened in severity and/or frequency or change in nature any time during the study. If the participant has a preexisting medical history of angioedema and this condition worsens during the study, it should be reported as an AE or SAE. Any new onset of angioedema in the participant with no prior occurrence should also be reported as an AE or SAE.

Any other AE not listed as an expected event in the IB or in this protocol will be considered unexpected.

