#### **Events NOT meeting the AE definition**

- Any clinically significant abnormal laboratory findings or other abnormal safety assessments which are associated with the underlying disease, unless judged by the Investigator to be more severe than expected for the participant's condition.
- The disease/disorder being studied or expected progression, signs, or symptoms of the disease/disorder being studied, unless more severe than expected for the participant's condition.
- Medical or surgical procedure (eg, endoscopy, appendectomy): the condition that leads to the procedure is the AE.

- Situations in which an untoward medical occurrence did not occur (social and/or convenience admission to a hospital).
- Anticipated day-to-day fluctuations of pre-existing disease(s) or condition(s) present or detected at the start of the study that do not worsen.

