## **DEFINITION OF SAE**

If an event is not an AE per definition above, then it cannot be an SAE even if serious conditions are met (eg, hospitalization for signs/symptoms of the disease under study, death due to progression of disease).

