**A SAE is defined as any untoward medical occurrence that, at any dose:**

**a) Results in death**

**b) Is life-threatening**

The term “life-threatening” in the definition of “serious” refers to an event in which the participant was at risk of death at the time of the event. It does not refer to an event, which hypothetically might have caused death, if it were more severe.

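### Protocol Appendix 3 gives opposite rules on whether lack of efficacy is an adverse event, and no text says which one prevails (minor)

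*Protocol*

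**What the plan says.** The conflict lies in the last two bullets under the heading on events that meet the AE definition, in Protocol Section 10.3 (Appendix 3). The first states that lack of efficacy, or failure of the expected pharmacological action, "per se will not be reported as an AE or SAE. Such instances will be captured in the efficacy assessments". It adds that resulting signs, symptoms or sequelae are reported if they meet the definition in their own right. The second bullet repeats that addition and then says of the same two terms that this "also constitutes an AE or SAE".

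Four other places bear on the point:

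- Section 8.3 makes the appendix operative: "The definitions of an AE or SAE can be found in Appendix 3".
- Section 8.3.6 limits reporting of the disease itself: "The CSU should be reported as an AE or SAE only if judged by the Investigator to have unexpectedly worsened in severity and/or frequency", or to have changed in nature.
- The appendix's list of events that are not AEs includes "The disease/disorder being studied or expected progression, signs, or symptoms of the disease/disorder being studied, unless more severe than expected" for the participant's condition.
- The SAE definition opens with a condition: "If an event is not an AE per definition above, then it cannot be an SAE even if serious conditions are met".

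Downstream, Protocol Section 3 (Table 2) makes the percentage of participants with treatment-emergent AEs or SAEs a secondary endpoint. Section 4.7.2 of the Study C SAP tabulates treatment-emergent AEs, and attaches risk differences and hazard ratios with 95% confidence intervals to the overview table and to the common preferred terms.

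**The concern.** A definition that every site must apply gives two answers to one question. A participant whose urticaria simply fails to improve has no reportable event under the first bullet and has one under the second. If sites differ in which bullet they follow, the same clinical course is an AE at one site and only a diary score at another.

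What is at stake is the meaning of the safety tables. Non-response is an efficacy outcome that the daily diary already measures. Entering it as an AE at some sites would mix efficacy into a safety endpoint, and would do so unevenly.

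**Working it through.** No alpha, power or event count is involved, so the check is a comparison of texts.

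**1. Do the bullets address the same thing?** Yes. Both name lack of efficacy and failure of expected pharmacological action. Neither is confined to a study, region or product. On signs, symptoms and sequelae they agree, so the conflict is only about lack of efficacy taken by itself.

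**2. Is the text current?** Yes. It stands in the body of Appendix 3. The Appendix 3 change logged in the history for Amended Protocol 02 concerns participant identifiers on copied source documents and does not touch these bullets.

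**3. Does any other text decide between them?**

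| Text | Names lack of efficacy? | Direction |
|---|---|---|
| Appendix 3, first bullet | Yes | Not an AE or SAE |
| Appendix 3, second bullet | Yes | Is an AE or SAE |
| Section 8.3.6 | No | Leans to the first bullet |
| Appendix 3, events that are not AEs | No | Leans to the first bullet |
| Appendix 3, SAE definition, opening condition | No | Neutral |
| Study C SAP 4.7.2 | No | Silent; TEAEs are set by timing |

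The rest of Section 8.3, the remainder of Appendix 3, the amendment history and the safety sections of the Study A and Study B SAPs give no rule of precedence either.

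The SAE condition is neutral because it applies only to an event already found not to be an AE. Its example of hospitalization for signs or symptoms of the disease under study falls inside that condition. Whether lack of efficacy is an AE is the open question, so this sentence cannot answer it.

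**4. A test case.** Take a participant whose urticaria continues at baseline level, neither worse nor changed in nature. The first bullet, Section 8.3.6 and the exclusion list give no AE. The second bullet gives an AE. A site cannot comply with both.

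**5. Would such a report reach the analysis?** Yes. The Study C SAP classes an AE as treatment-emergent from when it developed, worsened or became serious, and has no exclusion for lack-of-efficacy terms. The report would count in the any-TEAE row and in the preferred-term tables. If the preferred term reached 2% in either group, it would also receive its own risk difference and hazard ratio.

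**6. Would it inflate SAE counts?** Much less readily. The wording "A SAE is defined as any untoward medical occurrence that, at any dose" is followed by a list of outcomes, such as death, threat to life or hospitalization. Plain non-response does not by itself meet one. The exposure is therefore mainly in non-serious counts, and that inference rests on the seriousness criteria alone.

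**The case against.** The best reply is that the ambiguity is narrow in practice. Non-response in this trial means continuing urticaria. Section 8.3.6 is in the protocol body, is written for this disease, and restricts its reporting to unexpected worsening or a change in nature. The exclusion list points the same way, and the governing AE definition requires an untoward medical occurrence. The Study C SAP also deals with lack of efficacy elsewhere, as a reason for stopping treatment that determines how a missing Week 24 value is imputed. On this view one half-sentence stands against everything else. It may be leftover template text: it follows a repeated sentence, and a note to Table 10 in Appendix 2 still contains an unfilled insertion prompt.

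Most of this stands, and it is why the point is minor. It does not remove the conflict. The texts that lean towards the first bullet do not mention lack of efficacy, and the text that does mention it says both things. The template explanation is an inference and gives a site no instruction.

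Two further replies are also right. Nothing in the documents shows that any site reported plain non-response as an AE. And the weight one participant carries in an arm's percentage is the same for any AE term, so it measures nothing about this defect.

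**Conclusion.** The contradiction is certain as a matter of text. How often sites would act on the second bullet is unknown, and neither the size nor the direction of any effect on the Study C tables can be established. The consequence is minor. Study C SAP Section 4.7 describes the safety analysis as essentially descriptive with no testing, and preferred-term tables would show the terms. The conclusion assumes only that some sites might read the second bullet literally.

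Three stronger readings are tempting and are not supported:

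- A reader might take the Study A figures for CSU reported as a treatment-emergent AE (8.8% placebo, 4.3% dupilumab) as evidence of the problem. Those reports may be valid under Section 8.3.6, and the protocol does not say how many, if any, reflect lack of efficacy.
- A reader might infer that efficacy results are compromised, for example because calling non-response an AE could change the recorded reason for stopping treatment and so the imputation method. No text links the AE definition to the coding of that reason. Alpha, power and the primary analysis are not shown to be affected.
- A reader might take the opening condition of the SAE definition as a safeguard for SAE counts. It is not one, for the reason given in the check above.

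**What to change.** The sponsor should reconcile the two bullets with each other, with Section 8.3.6, with the list of events that are not AEs and with the opening of the SAE definition, so that a single rule on lack of efficacy remains. The duplicated sentence should be deleted. Which rule is kept is for the sponsor to decide.

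If Study C sites are still collecting AEs, they should receive a dated clarification. The benefit is essentially confined to Study C: Protocol Section 2.1 reports Study A as completed and Study B treatment as being stopped.

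The work is a correction to one list and one site communication; no new safety table is needed. There are two costs. The change may have to pass through the amendment and IRB/IEC process in Section 10.1.1. And because the Study C SAP gives 02 Aug 2022 as the date of first randomization, reporting could differ before and after the clarification, so its date should be kept with the study records.

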#### **Events NOT meeting the AE definition**

- Any clinically significant abnormal laboratory findings or other abnormal safety assessments which are associated with the underlying disease, unless judged by the Investigator to be more severe than expected for the participant's condition.
- The disease/disorder being studied or expected progression, signs, or symptoms of the disease/disorder being studied, unless more severe than expected for the participant's condition.
- Medical or surgical procedure (eg, endoscopy, appendectomy): the condition that leads to the procedure is the AE.

- Situations in which an untoward medical occurrence did not occur (social and/or convenience admission to a hospital).
- Anticipated day-to-day fluctuations of pre-existing disease(s) or condition(s) present or detected at the start of the study that do not worsen.

## **DEFINITION OF SAE**

If an event is not an AE per definition above, then it cannot be an SAE even if serious conditions are met (eg, hospitalization for signs/symptoms of the disease under study, death due to progression of disease).

**A SAE is defined as any untoward medical occurrence that, at any dose:**

**a) Results in death**

**b) Is life-threatening**

The term “life-threatening” in the definition of “serious” refers to an event in which the participant was at risk of death at the time of the event. It does not refer to an event, which hypothetically might have caused death, if it were more severe.

**c) Requires inpatient hospitalization or prolongation of existing hospitalization**

In general, hospitalization signifies that the participant has been detained (usually involving at least an overnight stay) at the hospital or emergency ward for observation and/or treatment that would not have been appropriate in the physician’s office or outpatient setting. Complications that occur during hospitalization are AEs. If a complication prolongs hospitalization or fulfills any other serious criteria, the event is serious. When in doubt as to whether “hospitalization” occurred or was necessary, the AE should be considered serious.

Hospitalization for elective treatment of a pre-existing condition that did not worsen from baseline is not considered an AE.

**d) Results in persistent disability/incapacity**

- The term disability means a substantial disruption of a person’s ability to conduct normal life functions.
- This definition is not intended to include experiences of relatively minor medical significance such as uncomplicated headache, nausea, vomiting, diarrhea, influenza, and accidental trauma (eg, sprained ankle) which may interfere with or prevent everyday life functions but do not constitute a substantial disruption.

**e) Is a congenital anomaly/birth defect**

**f) Other situations:**

- Medical or scientific judgment should be exercised in deciding whether SAE reporting is appropriate in other situations such as important medical events that may not be immediately life-threatening or result in death or hospitalization but may jeopardize the participant or may require medical or surgical intervention to prevent one of the other outcomes listed in the above definition. These events should usually be considered serious.

- Examples of such events include invasive or malignant cancers, intensive treatment in an emergency room or at home for allergic bronchospasm, blood dyscrasias or convulsions that do not result in hospitalization, or development of drug dependency or drug abuse.

## RECORDING AND FOLLOW-UP OF AE AND/OR SAE

### AE and SAE recording

- When an AE/SAE occurs, it is the responsibility of the Investigator to review all documentation (eg, hospital progress notes, laboratory reports, and diagnostics reports) related to the event.
- The Investigator will then record all relevant AE/SAE information in the CRF.
- It is **not** acceptable for the Investigator to send photocopies of the participant's medical records to Sponsor's representative in lieu of completion of the AE/SAE CRF page.
- There may be instances when copies of medical records for certain cases are requested by Sponsor's representative. In such case, care should be taken to ensure that the patient's identity is protected and the patient's identifiers in the study are properly mentioned on any copy of a source document provided to the Company.
- The Investigator will attempt to establish a diagnosis of the event based on signs, symptoms, and/or other clinical information. Whenever possible, the diagnosis (not the individual signs/symptoms) will be documented as the AE/SAE.

### Assessment of intensity

The Investigator will make an assessment of intensity for each AE and SAE reported during the study and assign it to 1 of the following categories:

- Mild: An event that is easily tolerated by the participant, causing minimal discomfort and not interfering with everyday activities.
- Moderate: An event that causes sufficient discomfort and interferes with normal everyday activities.
- Severe: An event that prevents normal everyday activities. An AE that is assessed as severe should not be confused with a SAE. Severe is a category utilized for rating the intensity of an event; and both AEs and SAEs can be assessed as severe.

An event is defined as "serious" when it meets at least 1 of the predefined outcomes as described in the definition of an SAE, NOT when it is rated as severe.

### Assessment of causality

- The Investigator is obligated to assess the relationship between study intervention and each occurrence of each AE/SAE.
- A "reasonable possibility" of a relationship conveys that there are facts, evidence, and/or arguments to suggest a causal relationship, rather than a relationship cannot be ruled out.
- The Investigator will use clinical judgment to determine the relationship.
- Alternative causes, such as underlying disease(s), concomitant therapy, and other risk factors, as well as the temporal relationship of the event to study intervention administration will be considered and investigated.

- The Investigator will also consult the IB and/or Product Information, for marketed products, in his/her assessment.
- For each AE/SAE, the Investigator **must** document in the medical notes that he/she has reviewed the AE/SAE and has provided an assessment of causality.
- There may be situations in which an SAE has occurred and the Investigator has minimal information to include in the initial report to the Sponsor's representative. However, **it is very important that the Investigator always make an assessment of causality for every event before the initial transmission of the SAE data to the Sponsor.**
- The Investigator may change his/her opinion of causality in light of follow-up information and send a SAE follow-up report with the updated causality assessment.
- The causality assessment is one of the criteria used when determining regulatory reporting requirements.

### Follow-up of AEs and SAEs

- The Investigator is obligated to perform or arrange for the conduct of supplemental measurements and/or evaluations as medically indicated or as requested by the Sponsor to elucidate the nature and/or causality of the AE or SAE as fully as possible. This may include additional laboratory tests or investigations, histopathological examinations, or consultation with other health care professionals.
- If a participant dies during participation in the study or during a recognized follow-up period, the Investigator will provide the Sponsor with a copy of any post-mortem findings including histopathology, if available.
- New or updated information will be recorded in the originally completed CRF.
- The Investigator will submit any updated SAE data to the Sponsor within 24 hours of receipt of the information.

## REPORTING OF SAES

### SAE reporting to the Sponsor via an electronic data collection tool

- The primary mechanism for reporting an SAE to the Sponsor will be the electronic data collection tool.
- If the electronic system is unavailable, then the site will use the paper SAE data collection tool (see next section) in order to report the event within 24 hours.
- The site will enter the SAE data into the electronic system as soon as it becomes available.
- After the study is completed at a given site, the electronic data collection tool will be taken off-line to prevent the entry of new data or changes to existing data.
- If a site receives a report of a new SAE from a study participant or receives updated data on a previously reported SAE after the electronic data collection tool has been taken off-line, then the site can report this information on a paper SAE form (see next section) or to the Sponsor's representative by telephone.
- Contacts for SAE reporting can be found in the protocol.

